8.1. Efficacy Assessments

Planned time points for all efficacy assessments are provided in the SoA (Section 1.3). Clinical efficacy will be measured using the MG-ADL scale and quality of life will be measured using the MG-QoL15r and EQ-5D-5L.^{5,6}

8.1.1. MG-ADL

The MG-ADL is an 8-item patient-reported scale that assesses MG symptoms and their effects on daily activities. It evaluates a participant's capacity to perform different activities in their daily life, including talking, chewing, swallowing, breathing, brushing their teeth, combing their hair, or getting up from a chair. The MG-ADL also assesses double vision and eyelid droop. It is a discrete quantitative variable in which the 8 items are rated by the participant on a scale of 0 to 3. The total score can range from 0 to 24, with higher total scores indicating more impairment. The MG-ADL assessment does not require any equipment to perform. The scoring of the MG-ADL should be performed by a trained and certified evaluator. If possible, the same evaluator should administer the MG-ADL for a given participant throughout the study. It is recommended to perform the MG-ADL scale prior to all other assessments.

8.1.2. MG-QoL15r

The MG-QoL15r is a 15-item survey of a patient's perceived health-related quality of life and addresses attributes known to be meaningful to a patient with gMG, such as psychological well-being and social functioning.

The patient assesses statements using a 3-point (0–2) Likert scale on the following domains:

- mobility (9 items)
- symptoms (3 items)

- general contentment (1 item)
- emotional well-being (2 items)

Each item will be participant-scored using a 3-point severity scale ranging from 0 (not at all) to 2 (very much), with a maximum possible score of 30. The MG-QoL15r is helpful in determining the participant's perception of the extent and dissatisfaction of MG-related dysfunction.

8.1.3. EQ-5D-5L

The EQ-5D-5L is a standardized measure of health status and was developed by the EuroQoL Group to provide a simple, generic measure of health status for clinical and economic appraisal.

The descriptive system comprises 5 dimensions:

- mobility
- self-care
- usual activities
- pain/discomfort
- anxiety/depression

Each dimension has 5 levels:

- no problem
- slight problem
- moderate problem
- severe problem
- extreme problem

The participant will be asked to indicate his/her health state by ticking the (or placing a cross in) the box against the most appropriate statement in each of the 5 dimensions. This decision results in a 1-digit number expressing the level selected for that dimension. The digits for 5 dimensions were combined in a 5-digit number describing the respondent's health state. A unique health state is defined by combining 1 level from each of the 5 dimensions. A total of 3125 possible health states could be defined in this way. Each state is referred to in terms of a 5-digit code. For example, state 11111 would indicate no problems in any of the 5 dimensions, while state 12345 would indicate no problem with mobility, slight problems with washing or dressing, moderate problems with doing usual activities, severe pain or discomfort, and extreme anxiety or depression.

A VAS is included in the questionnaire. Participants are asked to mark the health status from 0 to 100 on the day the interview is conducted, with a score of 0 corresponding to "the worst health you can imagine" and 100 corresponding to "the best health you can imagine."

8.1.4. Pharmacodynamics

Total IgG levels and AChR antibody levels (in AChR-Ab seropositive participants only) will be measured using validated methods from blood samples as indicated in Section 1.3. The actual

date and time of the blood sample collection will be collected and included in the central laboratory data transfer.

8.2. Safety Assessments

Planned time points for all safety assessments are provided in the SoA (Section [1.3](#)).

8.2.1. Demography

Demography information will be copied over from antecedent studies ARGX-113-2001 and ARGX-113-1705.

8.2.2. Physical Examinations

A complete physical examination will include, at a minimum, assessments of the participant's general appearance, skin, lymph nodes, musculoskeletal/extremities, abdomen, cardiovascular, respiratory, and neurological systems. Investigators should pay special attention to clinical signs related to previous serious illnesses.

8.2.3. Vital Signs

Vital signs (to be taken before blood collection for laboratory tests) will include temperature, systolic and diastolic blood pressure, and pulse.

It is recommended that the method used to measure body temperature at study entry is maintained throughout the study.

Blood pressure and pulse measurements will be assessed in a semi-supine position with a completely automated device. Manual techniques will be used only if an automated device is not available.

Blood pressure and pulse measurements should be preceded by at least 5 minutes of rest for the participant in a quiet setting without distractions (eg, television, cell phones).

8.2.4. Electrocardiograms

Single 12-lead ECGs will be obtained predose on dosing days, using an ECG machine.

8.2.5. Medical and Surgical History

Medical history from the antecedent studies ARGX-113-2001, ARGX-113-1704, and ARGX-113-1705 will be used.

8.2.6. Clinical Safety Laboratory Assessments

See Section [10.2](#) for the list of clinical laboratory tests to be performed. The details of sampling, handling, storage, and transportation of the samples will be described in the laboratory manual. The actual sample collection date and time will be collected and included in the central laboratory data transfer.

The investigator must review the laboratory report, document this review, and record any clinically significant changes occurring during the study as an AE. The laboratory reports must be filed with the source documents.

All routine laboratory safety assessments must be performed by the central laboratory.

Abnormal laboratory findings associated with the underlying disease are not considered clinically significant unless judged by the investigator to be more severe than expected for the participant's condition.

All laboratory tests with values considered clinically significantly abnormal during participation in the study should be repeated until the values return to normal or baseline or are no longer considered clinically significant by the investigator or medical monitor.

- If any values do not return to normal/baseline within a period of time judged reasonable by the investigator, the etiology should be identified, and the sponsor notified.
- All protocol-required laboratory tests, as defined in Section 10.2, must be conducted in accordance with the laboratory manual and the SoA (Section 1.3).
- If laboratory values from nonprotocol specified laboratory tests performed at the institution's local laboratory require a change in participant management or are considered clinically significant by the investigator and an SAE, then it must be recorded on the SAE form.

8.2.6.1. Hematology, Clinical Chemistry, Coagulation Panel and Urinalysis

Clinical laboratory tests will be reviewed for potential clinically significant findings at all time points throughout the study. Findings meeting the definition of an AE (see Section 10.4) must be recorded on an AE page of the eCRF. See Section 10.4.3 for information on following up of clinically significant abnormalities

Laboratory tests with values considered clinically significantly abnormal during the study that meet the definition of an AE will be monitored until the values return to normal or baseline or are no longer considered clinically significant by the investigator or medical monitor.

8.2.6.2. SARS-CoV-2 Test

Nasal and throat mucosal cell samples will be collected according to the laboratory manual at the time points to be tested for SARS-CoV-2 as needed. Participants should only be tested if they have symptoms of COVID-19 or if they were in contact with someone who tested positive for SARS-CoV-2, unless local or site regulations have more stringent testing requirements. See Section 10.6.

8.2.7. Pregnancy Testing

Urine tests for pregnancy will occur for WOCBP at the time points specified in the SoA (Section 1.3). Pregnancy testing in WOCBP will be conducted at the end of relevant systemic exposure (ie, at the SFU).

Additional pregnancy testing could be performed as necessary by the investigator or as required by local regulations, to establish the absence of pregnancy at any time during the study.

8.2.8. Immunogenicity

8.2.8.1. ADA Against Efgartigimod

Blood samples will be collected to assess the serum levels of ADA against efgartigimod as indicated in the SoA (Section 1.3). Sampling will be done predose on IMP administration visits. The details of sampling, handling, storage, and transportation of the samples will be described in the laboratory manual.

As per regulations, all samples will be analyzed in a 3-tiered approach using validated methods:⁷

1. First, all samples will be evaluated in a screening assay (tier 1) and scored as ADA positive or negative
2. Samples that screen positive in tier 1 will be evaluated in the confirmatory ADA assay to assess the specificity of the ADA response. The samples will be scored as either confirmed positive (ie, positive immunodepletion) or confirmed negative (ie, negative immunodepletion).
3. Samples confirmed to be positive for ADA in tier 2 will be further analyzed in a titration assay to characterize the magnitude of the ADA response and a NAb assay to assess the ADA for neutralizing activity.

If no sample was taken, the reason will be recorded.

8.2.8.2. ADA Against rHuPH20

Blood samples will be collected to assess the plasma levels of ADA against rHuPH20 as indicated in the SoA (Section 1.3), including a sample taken at the first visit of the first TP (TP₁V1) for participants coming from study ARGX-113-1705 and for participants coming from study ARGX-113-2001 who received efgartigimod IV. Sampling will be done predose on IMP administration visits. The details of sampling, handling, storage, and transportation of the samples will be described in the laboratory manual. If no sample was taken, the reason will be recorded.

As per regulations, samples will be analyzed in a 3-tiered approach using validated methods:⁷

1. Samples will be analyzed in a screening assay (tier 1), which identifies putative positive or negative samples.
2. Samples that screen positive in tier 1 will be evaluated in the confirmatory ADA assay to assess the specificity of the ADA response. The samples will be scored as either confirmed positive or negative.
3. Samples confirmed to be positive for ADA in tier 2 will be further analyzed in a titration assay to characterize the magnitude of the ADA response, and a neutralizing antibody (NAb) assay to assess the ADA for neutralizing activity.

Samples taken during the second year will only be analyzed if needed for safety purposes.

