^j Additional blood samples (serum/PBMC) may need to be taken for additional/optional/future/vaccination research if the participant consents. If a participant who consents to this additional sampling receives a vaccination during the study, samples referred to in Section 8.2.9 should be taken. The closest visit that is at least 4 weeks after the vaccine was administered may be used. If this visit does not coincide with IPnV1, then another sample will also be taken at this visit. Serum samples only need to be taken when a vaccination is planned or after a vaccination has occurred. In addition, a whole-blood sample to isolate PBMCs will be collected at study entry and then approximately every 3 months throughout the study during a scheduled on-site visit, regardless of the vaccines a participant has received.

^k Titers of ADA and the presence of NAbs against efgartigimod will be measured in serum. Blood samples for plasma titer levels of ADA and NAbs against rHuPH20 will also be taken, but these will only be analyzed if needed for safety purposes.

^l A nasopharyngeal swab will be performed to sample nasal and throat mucosal cells. Participants should only be tested for SARS-CoV-2 if they have symptoms of COVID-19 or if they were in contact with a person who tested positive for SARS-CoV-2, unless local or site regulations have more stringent testing requirements. Participants may be retested as needed. See Section 10.6.

^m This activity is only for women of childbearing potential. See Section 10.5.2.1.

ⁿ Training can continue until the participant or caregiver is ready to administer efgartigimod PH20 SC, to the satisfaction of the site staff (a minimum of 1 visit) before performing an administration under the supervision of site staff. Therefore, a minimum of 2 visits is required for a participant or caregiver to be considered competent to administer efgartigimod PH20 SC at home. Caregivers must sign the ICF before being trained in IMP administration.

^o The first dose administration of all TPs (TPnV1) must be performed on-site, even if the dose is self-administered or administered by the caregiver. Subsequent administrations in any TP (TPnV2/3/4) may be performed at home, if the participant or caregiver has been trained and is competent to perform IMP administration. When IMP administration is performed at home, the associated visit will be performed by phone.

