2.4.1 Calculation of descriptive statistics and percentages

For continuous variables, full descriptive statistics will only be presented if there are at least 2 non-missing observations. Alternatively, only the number of non-missing data points and mean are shown.

Descriptive statistics will include the number of non-missing data points, the arithmetic mean, the standard deviation (SD, for general and safety) or standard error (SE, for PD and efficacy), the median, minimum, Q1, Q3, and maximum. In addition, for PD and efficacy analyses, the 95% 2-sided confidence interval may be provided. For immunogenicity, geometric mean and geometric coefficient of variation (CV%) will be added.

The 95% 2-sided confidence interval, arithmetic mean, geometric mean, median, Q1, and Q3, will be presented with one more decimal place than the individual values. SE and SD will be presented with two more decimal places than the individual values. The minimum and maximum will be presented with the same number of decimal places as the individual values. CV% will be presented with 2 decimal places.

Descriptive statistics for PK concentrations will include n (number of observed values), arithmetic mean, SD, median, minimum and maximum, and CV%.

Serum concentrations will be presented with 3 significant digits in the original concentration units, except values ≥ 1000 , which will be rounded to an integer. The descriptive statistics should be rounded to the same number of significant digits as the individual values. If more than half of the values are BLQ, SD and CV% will not be calculated.

For event-type safety data, the number and percentage of participants with an event will be shown. The denominator will be all participants in the analysis set per treatment and cycle. All cycles will be shown, even if no events are present.

For frequency tabulations and cross-tabulations, the denominator will be all participants in the analysis set per treatment. For tables where results are shown by analysis visit, the denominator will be all participants in the analysis set per treatment and per analysis visit. Missing values will never be included in the denominator count when computing percentages. For cross-tabulations of post-baseline results versus baseline results, a ‘missing’ category will be shown for baseline results if applicable. Similarly for immunogenicity correlation tables, a “missing ADA/NAb classification” category will be shown if applicable.

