4.5 IMMUNOGENICITY

4.5.1 Available data

Blood samples will be collected to assess the serum levels of ADA against efgartigimod and plasma levels to assess antibodies against rHuPH20. Sampling will be done predose on IMP administration visits.

Immunogenicity samples are analyzed in a 3-tiered approach:

- All samples are evaluated in the efgartigimod ADA or anti-rHuPH20 Ab screening assay and are scored screening positive or negative
- If a sample scored screening positive, it is further evaluated in the confirmatory assay and is scored confirmed positive (positive immunodepletion) or confirmed negative (negative immunodepletion).
- If a sample is scored as confirmed positive, the samples are further characterized in the titration assay (to determine titer) and are also further analyzed in the NAb (neutralizing antibodies) assay to confirm neutralizing activity. For NAb against efgartigimod, a screening assay is performed and results will be reported as negative or positive. For NAb against rHuPH20, the same 3-tiered approach is implemented: the screening NAb assay, followed by a NAb confirmatory assay, and a titer NAb assay. .

[figure not shown]
If available, a titer result will be reported for the confirmed positive samples.

However, a titer result is not always available:

- In case the confirmed positive sample could not be run in the titration assay (eg, due to insufficient sample volume/quality to perform the titer analysis), the result will be described as 'positive immuno-depletion' and the sample should be considered as positive.
- If a sample is negative in the titration assay, it will be reported as 'negative titer' but it should be considered as positive since it was confirmed positive in the second tier.
- If a sample could not be analyzed or reported as 'positive screen', the sample status is unevaluable.

An overview of this 3-tiered approach and all possible sample results that will be reported by the laboratory is given below. From these reported efgartigimod or anti-rHuPH20 Ab sample results a final ADA sample status needs to be derived during the statistical analysis, as presented in the final column ('Final Outcome'):

SGS	Statistical Analysis Plan	
ARGX-113-2002	Final Analysis	Final 5.0 of 31Jan2025

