^a missing screen includes the following terms (reported as reason not done): NA (not analyzed), NR (no result), NS (no sample) and SL (sample lost). More details can be found in the IS data transfer agreements from SGS France (for ADA against efgartigimod) and Labcorp Indianapolis (for antibodies against rHuPH20 and rHuPH20 NAb) to SGS SD office.

^b 'positive titer' is reported in case it was not possible to retrieve a numeric value.

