4.5.2.3 PARTICIPANT CLASSIFICATION FOR ANTIBODIES AGAINST RHUPH20

Table below gives an overview of how the anti-rHuPH20 antibody (rHuPH20 Ab) participant classification will be derived, starting from the participant baseline rHuPH20 Ab sample status.

Participant anti-rHuPH20 Ab classification	Highest ^c post baseline sample status			
	rHuPH20 Ab negative	rHuPH20 Ab positive (missing titer ^a)	rHuPH20 Ab positive ('negative titer' ^b or numeric titer value)	rHuPH20 Ab not evaluable
Baseline rHuPH20 Ab sample status				
rHuPH20 Ab negative	rHuPH20 Ab negative	Treatment Induced rHuPH20 Ab	Treatment Induced rHuPH20 Ab	rHuPH20 Ab unevaluable
rHuPH20 Ab positive (missing titer ^a)	Treatment Unaffected rHuPH20 Ab	rHuPH20 Ab unevaluable	rHuPH20 Ab unevaluable	rHuPH20 Ab unevaluable
rHuPH20 Ab positive ('negative titer' ^b or numeric titer value)	Treatment Unaffected rHuPH20 Ab	rHuPH20 Ab unevaluable	titer < 2 x baseline titer: Treatment Unaffected rHuPH20 Ab	titer ≥ 2 x baseline titer: Treatment Boosted rHuPH20 Ab ^d
rHuPH20 Ab not evaluable	rHuPH20 Ab unevaluable	rHuPH20 Ab unevaluable	rHuPH20 Ab unevaluable	rHuPH20 Ab unevaluable

^a Samples with missing titer have as reported rHuPH20 Ab result 'positive immunodepletion' or 'positive titer'.

^b Results reported as 'negative titer', ie, titer value <=5 will be set to value of 5;

^c Highest sample status, with order: (from low to high): rHuPH20 Ab unevaluable, rHuPH20 Ab negative, rHuPH20 Ab positive (missing titer/positive immunodepletion), rHuPH20 Ab positive with titer <= 5 ('negative titer' as reported rHuPH20 Ab result, titer value set to 5), rHuPH20 Ab positive with titer > 5 (ie, positive titer and selecting the sample with highest titer)

^d Note: Twofold difference in titer values is considered significant in case a twofold serial dilution is applied (reference to Shankar et al., 2014).

rHuPH20 Ab evaluable participant = participant classified as any of following categories: ADA negative, treatment-unaffected rHuPH20 Ab, treatment-induced rHuPH20 Ab, treatment-boosted rHuPH20 Ab.

rHuPH20 Ab unevaluable participant = participant classified as rHuPH20 Ab unevaluable or with missing baseline rHuPH20 Ab sample or without post-baseline rHuPH20 Ab samples

In case no rHuPH20 Ab data is available at all, the participant can not be classified.

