4.5.3 Presentation of results

Analyses will be done for ADA against efgartigimod and antibodies against rHuPH20.

Statistical Analysis Plan

ARGX-113-2002

Final Analysis

Final 5.0 of 31Jan2025

Frequency tabulations (number and percentages) will be provided with ADA or rHuPH20 Ab negative/positive/unevaluable samples per analysis visit. In addition, these tables will be repeated by overall ADA or rHuPH20 Ab participant classification.

Frequency tabulations (number and percentages) will be provided by cycle and overall on:

- participants per ADA or rHuPH20 Ab participant classification
- prevalence and incidence of ADA or rHuPH20 Ab
- ADA or rHuPH20 Ab unevaluable participants
- ADA or rHuPH20 Ab baseline (study 2002) positive/negative/unevaluable samples

For details on the definitions, see the above sections 4.5.2.2 and 4.5.2.3.

The ADA or rHuPH20 Ab participant category of the applicable cycle will be used for all tables. The baseline used for the ADA or rHuPH20 Ab participant classifications (the cycle and overall participant classification), is the 2002 study baseline.

The above frequency tabulations will be repeated for NAb assay using the definitions as defined in section 4.5.2.4 and 4.5.2.5.

Analysis will be performed for the overall safety population. The frequency tabulations on prevalence and incidence of ADA and NAb against efgartigimod will be repeated by cycle cohort (see section 2.4.4).

The frequency tabulations on prevalence and incidence of ADA against efgartigimod, and rHuPH20 Ab will also be shown by MG therapies (see section 3.5.2 and 3.5.3). Following categories will be shown: NSIDS, steroids, NSIDS+steroids, no NSIDS or steroids.

In addition, frequency tabulations (number and percentages) will be provided for:

- NAb against efgartigimod positive participants within the ADA participant classification against efgartigimod (Treatment-unaffected ADA, Treatment-induced ADA, Treatment-boosted ADA, ADA Negative, and ADA Unevaluable).
- rHuPH20 Ab positive participants within the ADA participant classification against efgartigimod.

ADA titer values against efgartigimod and rHuPH20 Ab titer values will be summarized by means of descriptive statistics by overall ADA participant classification against efgartigimod or rHuPH20 Ab participant classification, respectively.

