ⁱ Blood samples for clinical laboratory (hematology/clinical chemistry/coagulation panel and FSH, if applicable) safety assessments will be collected. See Section 10.2. Participants will need to be fasted for each on-site visit at which safety laboratory assessments are collected. Fasted is defined as no food or drink at least 8 hours prior to each sampling. Permitted medications that the participant normally takes can be taken as usual before a visit.

^j Additional blood samples (serum/PBMC) may need to be taken for additional/optional/future/vaccination research if the participant consents. If a participant who consents to this additional sampling receives a vaccination during the study, samples referred to in Section 8.2.9 should be taken. The closest visit that is at least 4 weeks after the vaccine was administered may be used. If this visit does not coincide with IPnV1, then another sample will also be taken at this visit. Serum samples only need to be taken when a vaccination is planned or after a vaccination has occurred. In addition, a whole-blood sample to isolate PBMCs will be collected at study entry and then approximately every 3 months throughout the study during a scheduled on-site visit, regardless of the vaccines a participant has received.

^k Titers of ADA and the presence of NAbs against efgartigimod will be measured in serum. Blood samples for plasma titer levels of ADA and NAbs against rHuPH20 will also be taken, but these will only be analyzed if needed for safety purposes.

^l A nasopharyngeal swab will be performed to sample nasal and throat mucosal cells. Participants should only be tested for SARS-CoV-2 if they have symptoms of COVID-19 or if they were in contact with a person who tested positive for SARS-CoV-2, unless local or site regulations have more stringent testing requirements. Participants may be retested as needed. See Section 10.6.

^m This activity is only for women of childbearing potential. See Section 10.5.2.1.

ⁿ Training can continue until the participant or caregiver is ready to administer efgartigimod PH20 SC, to the satisfaction of the site staff (a minimum of 1 visit) before performing an administration under the supervision of site staff. Therefore, a minimum of 2 visits is required for a participant or caregiver to be considered competent to administer efgartigimod PH20 SC at home. Caregivers must sign the ICF before being trained in IMP administration.

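### From year 2, rHuPH20 antibody samples are assayed only on safety need, yet the SAP says all samples are screened and reports by-cycle and overall rates with no limit to the routinely assayed period

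*Protocol*

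**What the plan says.** Three places restrict the assay. Protocol 8.2.8.2 states: "Samples taken during the second year will only be analyzed if needed for safety purposes". Protocol section 1.3, Table 2 (year 2 onward), footnote k keeps the blood draws but adds that "these will only be analyzed if needed for safety purposes". SAP appendix 9.4.2, footnote k carries the same rule: samples "will also be taken, but these will only be analyzed if needed for safety purposes". The first of these names only the second year; the other two cover year 2 onward.

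SAP 4.5.1 reads differently: "All samples are evaluated in the efgartigimod ADA or anti-rHuPH20 Ab screening assay", with no limit by year. The protocol does separate the two analytes. Section 8.2.8.1 has all efgartigimod ADA samples assayed, while 8.2.8.2 omits the word all for rHuPH20 and adds the restriction.

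On reporting, SAP 4.5.3 says: "Frequency tabulations (number and percentages) will be provided by cycle and overall on" classification, prevalence and incidence, unevaluable participants and baseline status. It repeats this for neutralizing antibodies (NAb). The outputs are Table 14.2.6.9 (rHuPH20 Ab) and Table 14.2.6.20 (rHuPH20 NAb), with evaluable participants as denominator (SAP 4.5.2.3 and 4.5.2.5). AE tables by cycle rHuPH20 Ab class are 14.2.7.4.6, .12, .18 and .22.

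On status, SAP 4.5.2.3, footnote c ranks post-baseline results as follows: "Highest sample status, with order: (from low to high): rHuPH20 Ab unevaluable, rHuPH20 Ab negative", with the positive categories above. A note in 4.5.1 adds: "missing screen includes the following terms (reported as reason not done): NA (not analyzed", alongside codes for no result, no sample and lost sample.

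**The concern.** Incidence and prevalence over time of antibodies and NAb to rHuPH20 are secondary endpoints (protocol section 3). A rate per cycle is interpretable when samples are assayed irrespective of what happened to the participant. From year 2 the rule is the reverse: a sample is assayed because a safety question has arisen. No passage separates routine from safety-triggered results in these tables, or tells the reader which period they cover.

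There are two possible situations, and the plan handles neither.

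- Some later samples were assayed on safety grounds. Late-cycle rates then rest on a selected group. In the AE tables by antibody class, having an event may be the reason that a participant has a class at all.
- No later sample was assayed. There is then no selection, but the overall column covers the routinely assayed period only and will be read as whole-study incidence.

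**Working it through.** The plan gives no figure of its own for rHuPH20 antibody rates, so the check is a comparison of passages plus arithmetic on how much of the study is affected.

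**1. The text.** SAP 9.4.2 footnote k and SAP 4.5.1 cannot both be true of rHuPH20 samples from year 2. SAP 6.1 lists no departure from the protocol, so 4.5.1 does not read as a deliberate change.

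**2. The overall status.** Take a participant who is negative at baseline, negative on year 1 samples, and has later samples that were collected but not assayed.
- Each unassayed sample is apparently coded as not analyzed, hence unevaluable.
- The highest post-baseline status is chosen, and negative outranks unevaluable.
- The participant is therefore classed as negative and evaluable, stays in the denominator, and does not appear in the overall unevaluable count.

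In a late cycle taken alone, the same participant has no assayed sample and is unevaluable, so the loss does show there.

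**3. Share of cycles after year 1.** Inputs: four weekly doses span 21 days, and the year 1 minimum gap is 28 days (protocol 6.5.1), so the shortest on-schedule cycle is L = 21 + 28 = 49 days. The end of the last duration category in SAP 3.1 is day 1445. Assumptions: one participant, constant cycles, days counted from first dose, and L = 70 as a longer case.

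Cycles begun by day D = floor((D − 1)/L) + 1.

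| L | by 365 | by 730 | by 1095 | by 1445 |
|---|---|---|---|---|
| 49 | 8 | 15 | 23 | 30 |
| 70 | 6 | 11 | 16 | 21 |

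Share starting after day 365:
- L = 49: 7/15 = 47%, 15/23 = 65%, 22/30 = 73%.
- L = 70: 5/11 = 45%, 10/16 = 62.5%, 15/21 = 71%.
- A participant who leaves after 1 year has none.

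**4. Overall rate (assumed numbers).** Take 100 baseline-negative participants, of whom 20 convert in year 1. Of the other 80, let 0, 5 or 10 convert later with no later sample assayed. The table shows 20/100 = 20% with 0 unevaluable in each case. Full assay would give (20 + 0)/100 = 20%, (20 + 5)/100 = 25% or (20 + 10)/100 = 30%.

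**5. Late-cycle rate (assumed numbers).** With true prevalence p, and assay probabilities t1 in antibody-positive and t0 in antibody-negative participants, the reported rate is p·t1 / (p·t1 + (1 − p)·t0). For p = 10%:
- t0 = 5% and t1 = 5%: 0.005/0.050 = 10%
- t0 = 5% and t1 = 10%: 0.010/0.055 = 18%
- t0 = 5% and t1 = 20%: 0.020/0.065 = 31%
- t0 = 10% and t1 = 5%: 0.005/0.095 = 5%

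The result can fall on either side of the truth, and the documents give no value for t0 or t1.

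**The case against.** The strongest reply is that the SAP already shows what is missing. It carries the restriction in its own appendix and has a not-analyzed code. Negative, positive and unevaluable samples are tabulated per visit, and unevaluable participants per cycle. The correlation tables have a "missing ADA/NAb classification" category, and every result is listed. A fall in assayed samples would be visible by visit and by cycle. This stands. It does not, however, show why a sample was assayed, and it does not reach the overall rate.

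A second reply is that ranking unevaluable below negative is not peculiar to rHuPH20. Efgartigimod ADA uses the same order, and any overall incidence with unequal follow-up shares the limit. That is fair. The difference is that here the gap is created by rule, at a known point, in participants who are still being followed and sampled.

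Third, one rHuPH20 output is limited by period: Table 14.2.6.22, duration of response in the pre-amended phase. Its boundary is set by the cycle in which the v3.0 consent was signed, not by study year, and it is not a rate table.

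A reader might also infer that never-screened samples are counted as NAb negative. The documents do not support this. SAP 4.5.2.5 confines the default to antibody-negative samples and makes an unreported NAb sample unevaluable.

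**Conclusion.** The contradiction is plain in the text. As planned, the by-cycle rHuPH20 tables can mix routine and safety-selected results, and the overall rate can describe the routinely assayed period without saying so. This should be corrected because it limits what secondary-endpoint tables can support; the analysis is descriptive and no test depends on it.

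A reader might go further and conclude that late-cycle rates are inflated or that overall incidence is understated. The documents do not support either. They do not say whether any year 2 sample was assayed. They also do not say whether year 2 samples taken before v3.0 took effect in a given country were assayed routinely; the protocol's amendment summary applies v3.0 country by country. The size and direction of any bias are therefore unknown, and the rates in steps 4 and 5 are illustrations only.

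The cycle shares (45% to 47% at 2 years, 71% to 73% by day 1445) measure how many cycles fall outside year 1, not bias. They assume constant cycles with all doses given. Study time in the protocol runs from the first visit, so participants who begin in an intertreatment period have fewer year 1 cycles than shown. The mapping from laboratory result to final sample status is a figure not available here, so the coding of unassayed samples is inferred from the note in 4.5.1. The PK and IgG tables by rHuPH20 class are largely unaffected, because PK and PD are measured only in year 1.

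**What to change.** 1. Amend SAP 4.5.1 so that the all-samples statement does not apply to rHuPH20 samples from year 2 onward. Align the second-year wording of protocol 8.2.8.2 with the year 2 onward scope of Table 2.
2. Compute the headline rHuPH20 Ab and NAb incidence and prevalence, and the AE tables by rHuPH20 Ab class, on the routinely assayed period, and label the tables with that period. Cut at sample level, not cycle level: year 1 schedule samples, including a treatment period and following IPnV1 that cross into year 2 (note to protocol Table 2), plus any later samples assayed irrespective of events.
3. Show the version with all available results alongside. Give samples assayed and samples collected per cycle, and flag any safety-triggered result there and in listing 16.2.12.2, so that no triggered positive is hidden.

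The cost is a few SAP sentences, a second version of the affected tables and one sample-level flag. The documents provide for recording why a sample was not taken or not assayed, but not why one was assayed. That reason must come from the laboratory or be derived from the sample date; a date rule would also need to know when v3.0 took effect locally. The downside is that later cycles may show no headline rate.
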